5.5. Study Termination Criteria

The Sponsor may terminate the study for reasons of clinical significance, including but not limited to:

1. The study objectives have been achieved;

2. The incidence and severity of AEs in this study suggest that it is not appropriate to continue this clinical trial.

During the termination of the study, the Sponsor will ensure that the rights of the subjects are fully protected.

6. TREATMENTS ADMINISTRATED

6.1. Investigational Product

6.1.1. Acquisition

The investigational product 3D185 is provided by 3D Medicine (Beijing) Co., Ltd, for clinical studies.

6.1.2. Specification

3D185 are white to off-white, round, scored tablets. The dosage strength for clinical trials is 50 mg/tablets and 30 tablets/bottle.

6.1.3. Drug Labeling

The packaging and the sample labeling of the investigational product will be prepared in accordance with the Good Manufacturing Practice (GMP) and GCP regulatory requirements.

6.1.4. Product Storage

3D185 should be stored at room temperature $(15-25\mathbb{C})$, sealed and protected from light. Based on the currently stability data, the storage period of 3D185 is 2 years. The storage period can be extended according to further stability data. The investigational product should be stored as specified, and the storage temperature should be recorded and saved in the corresponding documents. All investigational products will be used in this study only and the protocol required operations.

6.1.5. Drug Accountability

A designated person is required to manage the reconciliation and recording of investigational products. The study center should ensure that there is a designee responsible for receiving the investigational product, that the drug treatment has an accurate record, and that the study drug is properly used and stored. Unused investigational products should be stored according to the requirements for drug storage. The fixed personnel will periodically check whether the storage meets the requirements. After completion of the study, all remaining drugs must be reconciled and recorded, then returned to the Sponsor to destroy.

6.2. Dosing Regimens and Methods

6.2.1. Dosing Regimens and Cycle

The starting dose in this study is 25 mg (half tablet). The preset seven dose-escalation cohorts are 25 mg, 50 mg, 100 mg, 150 mg, 200 mg, 250 mg, and 300 mg of 3D185 orally once a day, every 28 days in a treatment cycle. Eligible subjects in each cohort will receive a single oral dose of 3D185, followed by a 7-day washout period. Then, continue to receive the same dose of 3D185

until disease progression, death, toxicity intolerance, or withdraw informed consent, whichever comes first. At the end of each dose-escalation cohort, the PI and the Sponsor may work together to adjust the dose of the subsequent dose levels based on the safety data obtained from the previously completed cohorts.

Route of administration: (fasting) oral administration.

Treatment cycle: every 28 days in a treatment cycle.

6.2.2. Method of Administration

3D185 should be administered in accordance with the following principles:

- Subjects should be instructed to take 3D185 every morning with the same daily medication time;
- Subjects are advised to take 3D185 in a fasted state. No food should be consumed two hours before and two hours after the 3D185 dose;
- 3D185 should be swallowed with warm water;
- If vomiting occurs after taking 3D185, it is not required to make up for the dose, the subsequent dose should be taken in the next day. The occurrence and severity of vomiting during the treatment period must be recorded.

6.2.3. Delayed or Missed Dosing

If a dose of 3D185 is missed within 12 hours of the scheduled medication time, it can be taken as soon as possible on the same day. If a dose is missed more than 12 hours of scheduled medication time, it is not allowed to make up for the missed dose. Subject can resume the regular daily dose schedule in the next day. The medication interval must be more than 12 hours.

All cases of delayed or missed dosing must be recorded in the subject log and reported in the eCRF. The remaining tablets must be returned to the Investigator at the end of each cycle.

6.2.4. Overdose

Study treatment overdose is the accidental or intentional use of 3D185 in an amount higher than the protocol required dose.

When an overdose occurs, the Investigator should discuss with the sponsor's medical monitor and provide appropriate supportive care for drug overdose induced adverse reactions. The Investigator also should promptly report the adverse reactions to the Sponsor.

6.3. Precautions and Dose Modifications

6.3.1. Precautions

According to preclinical study results of 3D185, the possible toxicity of 3D185 included hyperphosphatemia, liver function abnormalities, gastrointestinal abnormalities, and skeletal system disorders. Based on clinical study results of the similar selective FGFR inhibitors, the common toxicities include hyperphosphatemia, nail and mucosal abnormalities, gastrointestinal abnormalities, ocular abnormalities (including reversible RPED), fatigue, cough, elevated lipase, etc.

Therefore, it must be important to monitor the liver and kidney function, serum phosphate, and skeletal system in this study. The clinical symptoms and signs also should be observed strictly. Once any above abnormalities occur, the Investigator should provide timely and effective medical treatment based on the subject's specific condition.

♦ Hyperphosphatemia & Hypercalcemia Management Guideline

During the study treatment period (including the DLT assessment period), all subjects should restrict phosphate intake to 600-800 mg/day (see Appendix 5 for phosphorus-rich foods). Guidelines for the clinical management of elevated serum phosphate levels are presented in Table 4.

Hypercalcemia is also a known adverse event in patients who received selective FGFR inhibitor treatment. A hypercalcemia should be considered when serum calcium corrected for albumin level is above Upper Limit of Normal (ULN).

In case of grade 2 hypercalcemia concurrent with hyperphosphatemia or grade 3 hypercalcemia in absence of hyperphosphatemia, 3D185 should be discontinued permanently.

Serum Phosphate Level	Dose Modification	Medical Management
5.6-6.9 mg/dL (1.8-2.2 mmol/L)	Continue 3D185 at current dose level.	Restriction of phosphate intake to 600 – 800 mg/day. May consider sevelamer 800 mg to 1,600 mg 3 times a day (with food)
7.0-9.0 mg/dL (2.3-2.9 mmol/L)	Withhold ^a 3D185 treatment until the serum phosphate level returns to < 5.5 mg/dL. Resume at the same dose level. A dose reduction may be implemented for persistent ^b hyperphosphatemia ($\geq 7 \text{ mg/dL}$) if	Restriction of phosphate intake to 600 - 800 mg/day. Sevelamer 800 to 1,600 mg 3 times a day with food until phosphate level is < 5.5 mg/dL.

Table 4Guidelines for Management of Serum Phosphate Elevation

Serum Phosphate Level	Dose Modification	Medical Management
	clinically necessary.	
> 9.0 mg/dL (> 2.9 mmol/L)	Withhold ^a 3D185 treatment until the serum phosphate level returns to $< 5.5 \text{ mg/dL}$. Resume at the next lower dose level in case of serum phosphate level returns to below 5.5 mg/dL within 7 days. Reduce by two dose levels if it takes 7~28 days to return to below 5.5 mg/dL despite adequate medical management. A second dose reduction may be implemented if needed or clinically indicated for persistent ^b hyperphosphatemia (\geq 7 mg/dL) at every cycle.	Restriction of phosphate intake to 600 – 800 mg/day. Sevelamer up to 1,600 mg 3 times a day with food AND Acetazolamide 250 mg 2 or 3 times a day only until serum phosphate level returns to < 5.5 mg/dL.
> 10.0 mg/dL (> 3.2 mmol/L) or significant alteration in baseline renal function OR Grade 2 hypercalcemia concurrent with hyperphosphatemia	3D185 should be discontinued permanently. (In situations where the subject is having clinical benefit and the investigator and the sponsor's medical monitor agree that re-starting drug is in the best interest of the subject, the drug may be re- introduced at two dose levels lower if appropriate ^c . Follow other recommendations described above.)	Medical management as clinically appropriate.

Note: These are general guidelines that are based on emerging data of other selective FGFR inhibitors and and/or the experts in the field. The treating physicians must use clinical judgment and local standard of care to decide the best way to manage phosphate elevation. If Sevelamer hydrochloride (renagel) is not available, use of other phosphate binders (non-calcium containing) based on the local standard is recommended, including Sevelamer carbonate (Renvela) or lanthanum carbonate (Fosrenol). a. Drug interruptions for hyperphosphatemia suggested to be 7 days duration

b. Persistent hyperphosphatemia is considered to be more than 1 sequential phosphate value of \geq 7 mg/dL c. If a subject has been deriving benefit from treatment, and the investigator can demonstrate that reintroduction of study drug is in the best interest of the subject considering the terminal nature of the disease, the drug may be re-introduced at a lower dose and/or intensity if the medical monitor is in

Serum Phosphate Level	Dose Modification	Medical Management					
agreement with this assessment. With appropriate re-consenting, the subject can be retreated with a 2-dose level reduction as appropriate, along with appropriate clinical follow-up as designated by the investigator.							
The investigator should also have the subject re-consent, explaining that re-introduction of investigational product could lead to increased risk of recurrent toxicities							

♦ Ocular Toxicity Management Guideline

FGFR target therapy can cause ocular toxicities, including dry eye, central serous retinopathy (CSR)/retinal pigment epithelial detachments (RPED), blurred vision, visual impairment, etc.

Ophthalmological examinations, including non-contact intraocular pressure, slit lamps, fundus examinations, and optical coherence tomography, should be performed regularly during screening period, treatment period, and safety follow-up period.

If the subject has any ocular toxicity, (such as dry eye, blurred vision, visual impairment, etc.), it is recommended to consult an ophthalmologist in time. If the subject has any significant eye discomfort at the unscheduled visit time during treatment period and safety follow-up visit, the subject should contact the Investigator as soon as possible and visit the ophthalmology clinic if necessary.

Guidelines for Management of Eye Toxicity are presented to Table 5.

Grade and Definition	Dose Modification	Medical Management
Grade 1: Asymptomatic or mild symptoms; clinical or diagnostic observations only	Refer for an ophthalmologic examination. If an ophthalmologic exam cannot be performed within 7 days, withhold treatment of 3D185 until an examination can be performed. If there is no evidence of eye toxicity on ophthalmologic examination, continue 3D185 therapy at the same dose level. If diagnosis from ophthalmologic examination is keratitis or retinal abnormality such as CSR/RPED, withhold 3D185 until signs and symptoms have resolved to baseline or stabilized. After consultation with the medical monitor, resume 3D185 therapy at the next lower dose level when toxicity is completely resolved to baseline, or stabilized and asymptomatic in 4 weeks according to ophthalmologic examination. Monitor for recurrence every 1 to 2 weeks for a month and as clinically appropriate thereafter.	Refer the subject for an Ophthalmologic examination. For retinal pathology perform OCT as appropriate and consider referral to a retinal specialist for further evaluation. Follow specific treatment per the ophthalmologist's recommendation.
Grade 2: Moderate; minimal, local or noninvasive intervention indicated; limiting age appropriate instrumental activities of daily living (ADL)	Immediately withhold 3D185 therapy. If there is no evidence of drug-related corneal or retinal pathology on ophthalmologic examination, withhold 3D185 until signs and symptoms have resolved to baseline. Resume 3D185 therapy at the next lower dose level. If diagnosis from ophthalmologic examination is keratitis or retinal abnormality such as CSR/RPED, withhold 3D185 until signs and symptoms have resolved to baseline, stabilized, or subject is lost to	Refer subject to an ophthalmologist for evaluation with an ophthalmologic examination. For retinal pathology, perform OCT as appropriate and consider referral to a retinal specialist for further evaluation.

Table 5Guidelines for Management of Eye Toxicity

Grade 4: Sight- threatening consequences; urgent intervention indicated; blindness (20/200 or worse) in the affected eye	Permanently discontinue treatment with 3D185. Report as a serious adverse event and monitor resolution of the event until complete resolution, stabilization or the subject is lost to follow-up or withdraws consent (which ever happens first).	Promptly refer subject to an ophthalmologist for evaluation with an ophthalmologic examination. Follow specific treatment per the ophthalmologist's recommendation.
Grade 3: Severe or medically significant but not immediate sight- threatening; hospitalization or prolongation of existing hospitalization indicated; disabling; limiting self-care ADL	If the toxicity is Grade 3, report as a serious adverse event and permanently discontinue 3D185. If however the toxicity is Grade 3 and reversible (complete resolution or stabilization and asymptomatic) within 4 weeks and the subject is having clinical benefit, and the investigator and the sponsor's medical monitor agree that	
	follow-up or withdraws consent (which ever happens first). If toxicity is Grade 2 and reversible (complete resolution or stabilization and asymptomatic) within 4 weeks according to ophthalmologic examination, resume 3D185 therapy at the next lower dose level after consultation with the medical monitor. In the case of Grade 2 CSR/RPED lasting more than 4 weeks, permanently discontinuing 3D185 ^a .	Follow specific treatment per the ophthalmologist's recommendation.

a. If a subject has been deriving benefit from treatment, and the investigator can demonstrate that reintroduction of study drug is in the best interest of the subject considering the terminal nature of the disease, the drug may be re-introduced at a lower dose and/or intensity if the medical monitor is in agreement with this assessment. With appropriate re-consenting, the subject can be retreated with a 2-dose level reduction as appropriate, along with appropriate clinical follow-up as designated by the investigator. The investigator should also have the subject re-consent, explaining that re-introduction of investigational product could lead to increased risk of recurrent toxicities.

Guidelines for the Management of Dry Eye as follows:

General considerations: Avoid unnecessary exposure to sunlight, use sunglasses in bright light.

Prophylactic management: Frequent use of artificial tear substitutes is strongly recommended.

Reactive management:

20. Withhold 3D185 for grade 3 toxicity, until resolves to Grade 1 or baseline, then

may resume dose level lower. Permanently discontinue 3D185 for grade 4 toxicity

- 21. Artificial tear substitutes if not started, every 4 to 6 hours
- 22. Hydrating /lubricating eye gels and ointments
- 23. Severe treatment-related dry eye should be evaluated by an ophthalmologist

♦ Hepatotoxicity Management Guideline

In case of Grade 2 AST/ALT elevation in patients without liver metastasis or AST/ALT elevation \geq 3.0-5.0 folds over baseline value in patients with liver metastasis, withhold 3D185 until the level returns to grade \leq 1 or baseline, and the liver test should be evaluated at least twice a week. Restart treatment with 3D185 at the same dose level.

In case of total bilirubin ≥ 2 folds over ULN, withhold 3D185 until the level returns to CTCAE Grade ≤ 1 or baseline, and the liver test should be evaluated at least twice a week. Restart treatment with 3D185 at same dose level.

In case of Grade 3 AST/ALT elevation, subjects should withhold 3D185 until the AST/ALT level returns to CTCAE Grade ≤ 1 or baseline. If the AE resolves within 7 days, dosing may resume at the same dose level. If the AE resolves within 7-14 days, dosing may resume at the previous lower dose level or may be modified according to the Investigator's judgment. If the AE cannot resolve within 28 days, the treatment of 3D185 will be permanently discontinued. Liver enzymes should be monitored once a week when the subject receives 3D185 treatment again.

When a hepatic injury is suspected due to abnormal liver function test (such as Grade ≥ 3 AST/ALT elevation), it is recommended to perform a comprehensive assessment (liver imaging, liver function tests and pathogen tests, etc.) as soon as possible.

Abnormal values in AST and/or ALT concurrent with abnormal elevations in total bilirubin that meet the criteria outlined below in the absence of other causes of liver injury are considered

potential cases of drug-induced liver injury (potential Hy's law cases) and should always be considered important medical events, 3D185 must be discontinued immediately. The threshold of laboratory abnormalities for a potential case of drug-induced liver injury depends on the subject's individual baseline values and underlying conditions. Subjects who present with the following laboratory abnormalities (potential drug-induced liver injury) should be evaluated further to determine the etiology of the abnormal laboratory values definitively:

- Subjects with AST or ALT and total bilirubin baseline values within the normal range who subsequently present with AST or ALT values ≥ 3 folds over ULN concurrent with a total bilirubin value ≥ 2 folds over ULN with no evidence of hemolysis and an alkaline phosphatase value ≤ 2 folds over ULN.
- For subjects with preexisting ALT or AST or total bilirubin values above the ULN, the following threshold values should be used in the definition mentioned above:
 - ♦ For subjects with preexisting AST or ALT baseline values > ULN, AST or ALT value ≥ 2 folds over the baseline values and ≥ 3 folds over ULN, or ≥ 8 folds over ULN (whichever is smaller).

Concurrent with:

♦ For subjects with preexisting values of total bilirubin above the normal range: Total bilirubin increased from baseline by an amount of at least 1-fold over ULN or if the value reaches ≥ 3 folds over ULN (whichever is smaller). Exception to the bilirubin elevation is made if the subject has Gilbert's disease and the elevated bilirubin is predominantly unconjugated.

The subject should return to the investigational site and be evaluated as soon as possible, preferably within 48 hours from awareness of the abnormal results. This evaluation should include laboratory tests, detailed history, and physical assessment. It is highly recommended to consult a hepatologist. The possibility of hepatic neoplasia (primary or secondary) should be considered. In addition to repeating measurements of AST and ALT, laboratory tests should include albumin, creatine kinase, total bilirubin, direct and indirect bilirubin, gamma-glutamyl transferase, PT/INR, and alkaline phosphatase. A detailed history, including relevant information, such as review of ethanol, acetaminophen, recreational drug, and supplement consumption, family history, occupational exposure, sexual history, travel history, history of contact with a jaundiced person, surgery, blood transfusion, history of liver or allergic disease, and work exposure, should be collected. Further testing for acute hepatitis A, B, or C infection and liver imaging (e.g., biliary tract) may be warranted. All cases confirmed on repeat testing as meeting the laboratory criteria defined above, with no other cause for Liver Function Test (LFT) abnormalities identified at the time should be considered potential drug-induced liver injury event. Such potential drug-induced liver injury should be reported as SAEs. When there is no other reason to explain the elevation of liver enzymes (Hy's law confirmed), 3D185 must be permanently discontinued.

♦ Nephrotoxicity (Proteinuria) Management Guideline

During the study, once the urinary protein test $\geq 2+$ (Grade ≥ 2 proteinuria), the subject should withhold 3D185 with 24-hour urine protein quantitative test and urine sediment test to detect microscopic hematuria. Dosing may continue while waiting for test results. If urine protein <

2 g/24 h, dosing may resume at the same dose level and it is recommended to continuously monitor urine protein. If urine protein ≥ 2 g/24 h, withhold until urine protein is < 2 g/24 h, restart at the same dose level or previous lower dose level per Investigator judgment. If Grade ≥ 2 proteinuria persists more than 28 days, the treatment of 3D185 should be permanently discontinued.

If the urinary protein test $\ge 2+$ (Grade ≥ 2 proteinuria) experience second recurrence or nephrotic syndrome occurs, 3D185 should be permanently discontinued.

A nephrologist is recommended to consult, when any Grade 3 proteinuria or other risk factors (e.g., microscopic hematuria, high blood pressure, etc.) occur.

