6.3.2. Dose Delay/Dose Modification

During the DLT evaluation period of the dose escalation phase, subject can withhold 3D185 due to drug-related AEs. If the withholding time is more than 7 days, the AE will be considered as DLT. Unless DLT occurs, subject's dose of 3D185 will not be reduced during this period.

Treatment can be modified or terminated based on toxicity as described in Table 6. For phosphate, liver, eye, kidney toxicity, specific recommendations in the management guidelines are provided in Section 6.3.1.

Toxicity Grade	Action	Dose Modification After Resolution of Adverse Event
1	None	Continue same dose
2	None or consider withheld or discontinue	If withheld, restart at same dose or 1 dose lower, if necessary.
3	Withheld	Restart at 1 or 2 doses lower if recovery (to \leq Grade 1 or back to baseline for non-hematologic toxicity) is within 28 days. Discontinue drug if unresolved for >28 days.
4	Withheld or discontinue	Discontinue*

Table 6Dose Modification Guidelines

For general toxicity management:

- Subjects with any grade of toxicity (Grade 1 to 4) should be provided symptomatic treatment when applicable.
- Subjects may have more than 1 dose reduction.

- If 3D185 must be withheld for more than 28 days for a drug-related adverse event that fails to resolve to acceptable level (e.g., ≤ Grade 1 non-hematologic toxicity or back to baseline), treatment with 3D185 should be discontinued with the exception noted below.*
- In all cases of clinically significant impaired wound healing or imminent surgery or potential bleeding complications, it is recommended that dose administration be interrupted, appropriate clinical laboratory data be carefully monitored, and supportive therapy administered, where applicable. Dose administration may be restarted when it is considered safe and at an appropriate dose, according to the investigator's assessment.

*Exception: if a subject has been deriving benefit from treatment, and the investigator can demonstrate that re-introduction of study drug is in the best interest of the subject considering the terminal nature of the disease, the drug may be re-introduced at a lower dose and/or intensity if the medical monitor is in agreement with this assessment. With appropriate re-consenting, the subject can be retreated with a 2-dose level reduction as appropriate, along with appropriate clinical follow-up as designated by the investigator.

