6.3.3. Discontinuation criteria for study treatment

When the following 3D185 related severe or life-threatening AEs occur, the investigational product must be permanently discontinued.

- Drug-related Grade 3 AEs or Grade 2 CSR/RPED that cannot recover to Grade ≤ 1 or baseline levels by symptomatic treatment within 28 days;
- Any grade 4 toxicities;
- Recurrent ≥ 2 Grade proteinuria;
- Recurrent Grade 3 eye toxicity associated with vision changes;
- Hy's law confirmed drug-induced liver injury;
- Grade 2 hypercalcemia concurrent with hyperphosphatemia or ≥ Grade 3 hypercalcemia in absence of hyperphosphatemia;
- Other AEs that the Investigator judged to be inappropriate to continue dosing.

If a subject has been deriving benefit from treatment, and the investigator can demonstrate that reintroduction of study drug is in the best interest of the subject considering the terminal nature of the disease, the drug may be re-introduced at a lower dose and/or intensity if the medical monitor is in agreement with this assessment. With appropriate re-consenting, the subject can be retreated with a 2-dose level reduction as appropriate, along with appropriate clinical follow-up as designated by the investigator.

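### On a literal reading, Grade 3 hypercalcemia with hyperphosphatemia is not an immediate permanent stop, although Grade 2 with hyperphosphatemia and Grade 3 without it both are

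*Protocol*

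**What the plan says.** The calcium rule appears in three places in the protocol.

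- Section 6.3.1, text on hyperphosphatemia and hypercalcemia: "In case of grade 2 hypercalcemia concurrent with hyperphosphatemia or grade 3 hypercalcemia in absence of hyperphosphatemia, 3D185 should be discontinued permanently".
- Section 6.3.1, Table 4, last row. Permanent discontinuation applies when phosphate exceeds 10.0 mg/dL, or on "significant alteration in baseline renal function OR Grade 2 hypercalcemia concurrent with hyperphosphatemia".
- Section 6.3.3, list of mandatory permanent stops: "Grade 2 hypercalcemia concurrent with hyperphosphatemia or ≥ Grade 3 hypercalcemia in absence of hyperphosphatemia".

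The general rules around it are these.

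- Section 6.3.2, Table 6, Grade 3 row: withhold, then "Restart at 1 or 2 doses lower if recovery" occurs within 28 days; otherwise "Discontinue drug if unresolved for >28 days".
- Section 6.3.2, cross-reference: "For phosphate, liver, eye, kidney toxicity, specific recommendations in the management guidelines are provided in Section 6.3.1". Calcium is not in that list.
- Section 6.3.3, other entries: "Drug-related Grade 3 AEs or Grade 2 CSR/RPED that cannot recover to Grade ≤ 1 or baseline levels by symptomatic treatment within 28 days", and "Any grade 4 toxicities". A last entry leaves further stops to the investigator's judgment.

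**The concern.** A stopping rule for toxicity should not become milder as the toxicity becomes worse. Here the limb for raised calcium with raised phosphate names Grade 2 only, and the Grade 3 limb is confined to patients whose phosphate is not raised. Taken at the letter, a patient who goes from Grade 2 to Grade 3 calcium while phosphate stays high leaves the immediate permanent stop and enters a withhold-and-restart rule.

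The combination is foreseeable. Section 6.3.1 describes hypercalcemia as known for this drug class and lists hyperphosphatemia among the expected toxicities. The trial is multicentre and runs in two countries, so sites could apply the wording differently. At stake is whether a patient with the more severe combination may be restarted under the ordinary rule. After a permanent stop, by contrast, re-introduction is an exception that rests on clinical benefit, agreement of the medical monitor and renewed consent.

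**Working it through.** The plan gives no figure to reproduce, so the check is a comparison of rules. Each calcium grade (2, 3, 4), with and without hyperphosphatemia, is read against Section 6.3.1 (text and Table 4), Section 6.3.2 (Table 6) and Section 6.3.3. Phosphate is taken as at most 10.0 mg/dL with no significant renal change, because either of those is a separate permanent stop in Table 4.

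| Calcium grade | Hyperphosphatemia | Action as written | Source |
|---|---|---|---|
| 2 | no | no mandatory stop; withholding or discontinuing may be considered | Table 6 |
| 2 | yes | immediate permanent stop | 6.3.1, Table 4, 6.3.3 |
| 3 | no | immediate permanent stop | 6.3.1, 6.3.3 |
| 3 | yes | withhold; restart 1 or 2 levels lower if recovered within 28 days; mandatory stop only if unresolved after that | Table 6, 6.3.3 |
| 4 | no | immediate permanent stop | 6.3.3 |
| 4 | yes | immediate permanent stop | 6.3.3 |

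Immediate permanent stops: 1 (Grade 2 with) + 1 (Grade 3 without) + 2 (Grade 4) = 4 of 6. Grade 2 without hyperphosphatemia is the mildest combination, so its lighter handling is in order. Grade 3 with hyperphosphatemia is handled more mildly than both Grade 2 with it and Grade 3 without it. No other cell is out of order.

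Four other provisions could close the gap.

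1. **The cross-reference in Section 6.3.2.** It sends phosphate toxicity to Section 6.3.1, and this patient has raised phosphate. The calcium rule found there is the one that omits the case.
2. **The Table 4 phosphate rows.** They apply alongside Table 6. At 5.6-6.9 mg/dL the dose continues. At 7.0-9.0 mg/dL it is withheld until phosphate is below 5.5 mg/dL and then normally resumed at the same level. Above 9.0 mg/dL it is withheld and resumed one level lower if phosphate recovers within 7 days, or two levels lower if that takes 7 to 28 days. None of these rows is a permanent stop, and none depends on calcium.
3. **DLT status.** Section 4.5 exempts electrolyte disturbances other than phosphorus from the Grade 3 rule when they are controlled within 48 hours. It also lets a subject resume, at the same dose or one level lower, after a DLT that recovers to Grade 0-1 within 28 days. It adds no permanent stop.
4. **The 28-day and judgment entries in Section 6.3.3.** The first acts only after failure to recover. The second is discretionary.

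None of the four makes the combination an immediate permanent stop.

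**The case against.** The strongest reply is that a bare grade in this protocol can mean a floor. Section 6.3.1 writes grade 3 without a sign, and Section 6.3.3 states the same criterion with ≥. On that usage Grade 2 in the other limb would also mean Grade 2 or worse. The two limbs would then be a lower threshold when phosphate is raised and a higher one when it is not. That is very probably what was meant, and it is why the point is put as a literal reading. It does not settle the matter, because Section 6.3.3, which lists the mandatory stops, puts ≥ on one limb and leaves it off the other within the same bullet.

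Safeguards also exist and stand. Table 6 withholds the drug at Grade 3, an event unresolved after 28 days ends treatment, the investigator may stop at any time, and the note under Table 4 asks for clinical judgment.

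Three stronger readings are tempting, and the documents do not support them.

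- *Dosing continues through the event.* It does not: Table 6 requires withholding at Grade 3. Only the restart differs.
- *The restart dose exceeds the exceptional re-introduction dose by a fixed amount.* Table 4 and Section 6.3.3 make the two-level reduction after a permanent stop a matter of what is appropriate, and Section 6.3.3 also speaks of a lower dose and/or intensity. Table 6 itself allows two levels. Table 4 calls for two levels when phosphate above 9.0 mg/dL recovers slowly, and Section 4.5 mentions the same dose or one level lower after a DLT. No reliable difference in mg/day follows.
- *Grade 4 is uncovered as well.* It is not: Section 6.3.3 stops any Grade 4 toxicity.

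**Conclusion.** The point holds on the letter of the text. One of six combinations, Grade 3 hypercalcemia with hyperphosphatemia, is left out of the immediate permanent stops, although both the lower grade with hyperphosphatemia and the same grade without it are included. What is lost is the fixed stop: the patient may restart under Table 6 without the conditions attached to re-introduction after a permanent stop.

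This assumes phosphate of at most 10.0 mg/dL, no significant renal change, and a site that reads Grade 2 as Grade 2 only. How often the event would occur cannot be derived from the protocol. A reader might infer that the sponsor chose a milder rule on purpose; nothing in the text gives a reason for one, and a missing ≥ is the likelier explanation. It is a minor safety-rule correction that should be made. The dose-escalation rules, sample size and analysis are untouched.

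**What to change.** Change *Grade 2* to *Grade ≥ 2* in the limb for hypercalcemia with hyperphosphatemia in three places: the Section 6.3.1 text, the last row of Table 4, and Section 6.3.3. In the Section 6.3.1 text also change *grade 3* to *Grade ≥ 3* in the limb without hyperphosphatemia, so that it matches Section 6.3.3. Immediate permanent stops then cover 5 of the 6 combinations; only Grade 2 without hyperphosphatemia remains outside, as now. The cost is four small edits, with no change to design, sample size or analysis.
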